11.11 Duration of morning stiffness (DMS)

Morning stiffness is defined by the time elapsed between the time of usual awakening (even if not in the morning) and the time the study participant is as limber as he/she will be during a day involving typical activities. The study participant/caregiver will be asked the following question (Kirwan and Reeback, 1986):

“How long does it take, from the time you (your child) wake up, for you (your child) to become as limber as you (your child) will be?”

For those experiencing relief, the actual hours elapsed should be recorded no matter how long. The duration in hours and minutes will be recorded. For those study participants with unrelenting stiffness, 24 hours should be recorded.

Duration of morning stiffness will be assessed at Baseline and at every visit through the Early Discontinuation/End of Treatment Visit.

11.12 Faces Pain Scale-Revised (FPS-R)

The Faces Pain Scale-Revised (FPS-R) is a self-reported measure used to assess the intensity of children’s pain (Hicks et al, 2001). The original version of the scale consists of 7 faces increasing in pain intensity and approximating equal intervals as assessed by children (Bieri et al, 1990). Children have to select a level on the scale that matches their own pain. A numerical value is associated with the different levels on the scale. The FPS-R was adapted from the FPS in order to make scoring possible on the widely accepted 0 to 10 metric. It includes 6 faces (instead of 7). This tool has been validated for children aged 5 to 12 years

and will be assessed in children ages 5 to 11 years. Study participants enrolled at 5 to 11 years of age will continue with the FPS-R when reaching 12 years of age. Completion of the FPS-R will not be required for study participants enrolled at 2 to 4 years of age if they reach 5 years of age during the study.

The FPS-R is provided in Appendix 17.4. The FPS-R will be administered at Baseline and then daily during the first week of the study; at Weeks 4, 12, 16, 24, and then every 8 weeks thereafter (for study participants enrolled prior to Protocol Amendment 9, visit frequency changes to every 16 weeks instead of every 8 weeks following implementation of Protocol Amendment 8) through the Early Discontinuation/End of Treatment Visit. The questionnaire should be checked by site personnel for completeness.

11.13 Patient's Assessment of Arthritis Pain (JIA Pain VAS)

In the JIA Pain VAS, study participants aged 12 years or older are asked the following question "How much pain have you had because of your illness today (acute version)/in the past week (standard version)?" (as applicable). The study participant should then place a mark on a 100mm horizontal line to indicate the severity of the pain. This VAS 100mm line has as anchors 0mm representing "No Pain" and 100mm, "Very Severe Pain."

Both versions of the JIA Pain VAS are provided in Appendix 17.5 and Appendix 17.6. The Pain (VAS) will be completed at Baseline (acute and standard versions), daily during the first week of treatment (acute version); Weeks 4, 12, 16, 24, and then every 8 weeks thereafter (for study participants enrolled prior to Protocol Amendment 9, visit frequency changes to every 16 weeks instead of every 8 weeks following implementation of Protocol Amendment 8) through the Early Discontinuation/End of Treatment Visit (standard version). The scale should be checked by site personnel for completeness.

11.14 Fatigue Assessment Scale (NRS)

The study participant's level of tiredness (fatigue) will be assessed by the Fatigue Assessment Scale (numeric rating scale [NRS]) where the parent/caregiver are asked the following question:

"Please rate your child's fatigue (weariness, tiredness) during the past week on a scale of 0 to 10" where 0 is "No fatigue" and 10 is "Fatigue as bad as you can imagine."

The recall period for this instrument is the past week.

The Fatigue Assessment Scale is provided in Appendix 17.7. The Fatigue Assessment Scale will be assessed at Baseline, Weeks 1, 2, 4, 8, and then every 8 weeks thereafter (for study participants enrolled prior to Protocol Amendment 9, visit frequency changes to every 16 weeks instead of every 8 weeks following implementation of Protocol Amendment 8) and the Early Discontinuation/End of Treatment Visit. Preferably, the same parent/caregiver should complete the scale for each visit. The scale will not be completed if the study participant is not living with a parent/caregiver at least part-time, ie, the parent/caregiver is not able to answer the question appropriately. The scale should be checked by site personnel for completeness.

11.15 Juvenile Arthritis School Attendance and Caregiver Work Productivity Survey

The Juvenile Arthritis School Attendance and Caregiver Work Productivity Survey is a parent/caregiver-reported self-administered questionnaire, which captures information related to the impact of the disease on the child's ability to participate in school and social/after-school activities and evaluate the impact of disease on the parent or caregiver's productivity at their paid work and in the household. The same parent/caregiver should complete the questionnaire at each visit. The recall period, for the questions relating to the child's school attendance and parent/caregiver's work productivity, is the past 4 weeks. This survey collects information related to eg, the child's attendance to school, number of school days missed due to the disease, number of school days impacted due to the disease, level of difficulty in performing school activities, the parent or caregiver's employment status, number of days missed from work due to the child's disease, number of days with work productivity reduced by half or more due to child's disease, days with no household work due to child's disease, days with productivity within household reduced by half or more due to child's disease. For further information please see the instructions provided on the worksheet.

The Juvenile Arthritis School Attendance and Caregiver Work Productivity Survey (parent/caregiver) will be assessed at Baseline, Week 4 and every visit through the Early Discontinuation/End of Treatment Visit. The full questionnaire and instructions are provided in Appendix 17.8.

12 STUDY MANAGEMENT AND ADMINISTRATION

12.1 Adherence to protocol

The Investigator should not deviate from the protocol. In medical emergencies, the Investigator may use his/her medical judgment and may remove a study participant from immediate hazard before notifying UCB (or its representative) and the IRB/IEC in writing regarding the type of emergency and the course of action taken.

12.2 Monitoring

UCB (or designee) will monitor the study to meet the Sponsor's monitoring Standard Operating Procedures (SOPs), ICH-GCP guidelines, and applicable regulatory requirements, and to ensure that study initiation, conduct, and closure are adequate. Monitoring of the study may be delegated by UCB to a contract research organization (CRO) or a contract monitor.

The Investigator and his/her staff are expected to cooperate with UCB (or designee) and to be available during the monitoring visits to answer questions sufficiently and to provide any missing information. The Investigator(s)/institution(s) will permit direct access to source data/documents for study-related monitoring, audits, IRB/IEC review, and regulatory inspection(s).

The Investigator will allow UCB (or designee) to periodically review all CRFs and corresponding source documents (eg, hospital and laboratory records for each study participant). Monitoring visits will provide UCB (or designee) with the opportunity to evaluate the progress of the study, verify the accuracy and completeness of CRFs, ensure that

all protocol requirements, applicable authorities regulations and Investigator's obligations are being fulfilled, and resolve any inconsistencies in the study records.

12.2.1 Definition of source data

All source documents must be accurate, clear, unambiguous, permanent, and capable of being audited. They should be made using some permanent form of recording (ink, typing, printing, optical disc). They should not be obscured by correction fluid or have temporary attachments (such as removable self-stick notes). Photocopies of CRFs are not considered acceptable source documents.

Source documents are original records in which raw data are first recorded. These may include hospital/clinic/general practitioner records, charts, diaries, x-rays, laboratory results, printouts, pharmacy records, care records, ECG or other printouts, completed scales, or Quality of Life Questionnaires, for example. Source documents should be kept in a secure, limited access area.

Some data will be recorded directly in the CRF and will not appear in a source document as defined in the Source Data Verification (SDV) form.

Source documents that are computer-generated and stored electronically do not need to be printed if the electronic medical record system at the investigational site is 21CFR Part 11 compliant. If the system is not 21CFR Part 11 compliant, the source data must be printed for review by the monitor (eg, ECG reports). Once printed, these copies should be signed and dated by the Investigator and become a permanent part of the study participant's source documents. The Investigator will authorize the monitor to compare the content of the printout and the data stored in the computer to ensure all data are consistent.

Electronic data records such as Holter monitor records or electroencephalogram records must be saved and stored as instructed by UCB (or designee).

12.2.2 Source data verification

Source data verification ensures accuracy and credibility of the data obtained. During monitoring visits reported data are reviewed with regard to being accurate, complete, and verifiable from source documents (eg, study participant files, recordings from automated instruments, tracings [ECG], x-ray films, laboratory notes).

The procedures for conducting SDV on computerized study participant records (if the system is 21CFR Part 11 compliant) are the same as those for paper records. Source data verification is performed by reviewing the electronic record directly.

All data reported on the CRF should be supported by source documents, unless otherwise specified in Section [12.2.1](#).

12.3 Data handling

12.3.1 Case report form completion

This study will use RDC. The Investigator is responsible for prompt reporting of accurate, complete, and legible data in the electronic CRFs and in all required reports.

Any change or correction to the CRF after saving must be accompanied by a reason for the change.

Corrections made after the Investigator's review and approval (by means of a password/electronic signature) must be reapproved by the Investigator.

The Investigator should maintain a list of personnel authorized to enter data into the electronic CRF.

Detailed instructions will be provided in the CRF Completion Guidelines.

12.3.2 Database entry and reconciliation

Case report forms/external electronic data will be entered/loaded in a validated electronic database using a clinical data management system (CDMS). Computerized data cleaning checks will be used in addition to manual review to check for discrepancies and to ensure consistency of the data. The data are entered into the electronic CRFs once and are subsequently verified.

An electronic audit trail system will be maintained within the CDMS to track all data changes in the database once the data has been saved initially into the system or electronically loaded. Regular backups of the electronic data will be performed.

12.3.3 Study participant screening and enrollment log/Study participant identification code list

The study participant's screening and enrollment will be recorded in the study participant screening and enrollment log.

The Investigator will keep a study participant identification code list. This list remains with the Investigator and is used for unambiguous identification of each study participant.

The study participant's consent and enrollment in the study must be recorded in the study participant's medical record. These data should identify the study and document the dates of the study participant's participation.

12.4 Termination of the study

A futility analysis of the PedACR30 response rate was performed after all active study participants on the reduced CZP dose had completed the Week 16 (Visit 8) assessments. If less than 50% of the study population enrolled on the reduced CZP dose regimen (Protocol Amendment 5) achieved a PedACR30 response at Week 16, the study was to be discontinued. The futility analysis confirmed that $\geq 50\%$ of the study population enrolled on the reduced CZP dose regimen achieved a PedACR30 response at Week 16. A further futility analysis will not be performed using the additional participants that will be enrolled on the original CZP dose regimen following the implementation of Protocol Amendment 9.

UCB reserves the right to temporarily suspend or prematurely discontinue this study either at a single site, multiple sites, or at all sites at any time for reasons including, but not limited to, safety or ethical issues, inaccurate or incomplete data recording, noncompliance, or unsatisfactory enrollment with respect to quality or quantity.

If the study is prematurely terminated or suspended, UCB (or its representative) will inform the Investigators/institutions, and the regulatory authority(ies) of the termination or suspension and the reason(s) for the termination or suspension, in accordance with applicable regulatory requirement(s). The IRB/IEC should also be informed and provided with reason(s) for the termination or suspension by the Sponsor or by the Investigator/institution, as specified by the applicable regulatory requirement(s). In addition, arrangements will be made for the return of all unused investigational products and other material in accordance with UCB procedures for the study.

12.5 Archiving and data retention

The Investigator will maintain adequate records for the study including CRFs, medical records, laboratory results, informed consent documents, drug dispensing and disposition records, safety reports, information regarding participants who discontinued, and other pertinent data.

All essential documents are to be retained by the Investigator until at least 2 years after the last approval of a marketing application in an ICH region and until there are no pending or contemplated marketing applications in an ICH region, or at least 2 years have elapsed since the formal discontinuation of clinical development of the investigational product. These documents should be retained for a longer period; however, if required by the applicable regulatory requirement(s) or by an agreement with UCB (ICH-GCP Guideline, Section 4.9.5). The Investigator will contact UCB for authorization prior to the destruction of any study records or in the event of accidental loss or destruction of any study records. The Investigator will also notify UCB should he/she relocate or move the study-related files to a location other than that specified in the Sponsor's study master file.

12.6 Audit and inspection

The Investigator will permit study-related audits mandated by UCB and inspections by domestic or foreign regulatory authorities, after reasonable notice.

The main purposes of an audit or inspection are to confirm that the rights and well-being of the study participants enrolled have been protected, that enrolled study participants (ie, signing consent and undergoing study procedures) are appropriate for the study, and that all data relevant for the evaluation of the IMP have been processed and reported in compliance with the planned arrangements, the protocol, investigational site, and IRB/IEC SOPs, ICH/GCP, and applicable regulatory requirements.

The Investigator will provide direct access to all study documents, source records, and source data. If an inspection by a regulatory authority is announced, the Investigator will immediately inform UCB (or designee).

12.7 Good Clinical Practice

Noncompliance with the protocol, ICH/GCP, or local regulatory requirements by the Investigator, institution, institution staff, or designees of the Sponsor will lead to prompt action by UCB to secure compliance. Continued noncompliance may result in the termination of the site's involvement in the study.

13 STATISTICS

A description of statistical methods is presented below and will be described in more detail in the Statistical Analysis Plan (SAP). Any deviations from the final SAP, as well as changes from the protocol, will be detailed in the Clinical Study Report.

13.1 Definition of analysis sets

- The Enrolled Set (ES) will consist of all study participants who have given informed consent.
- The Safety Set (SS) will consist of all study participants in the ES who have received at least 1 dose of study medication.
- The Full Analysis Set (FAS) will consist of all study participants in the SS who have a valid Baseline and valid post-Baseline efficacy measurement.
- The Pharmacokinetic Per-Protocol (PK-PP) Population is a subset of the SS consisting of those study participants who took at least 1 dose of study medication, provided measurable plasma samples (with recorded sampling time) on at least 1 occasion and who had no important protocol deviations affecting the PK parameters, as confirmed during a preanalysis review prior to locking the database. This population will be used for the PopPK model and for all presentations of plasma concentration and PK data.
- The Pharmacokinetic-Pharmacodynamic (PK-PD) Population will consist of all study participants in the SS who have at least 1 post-Baseline plasma concentration measurement and 1 post-Baseline PedACR30 assessment.

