4.2 Secondary variables

Efficacy will be assessed by the PedACR30, PedACR50, PedACR70, and PedACR90 response rates at Week 16 as compared to Baseline (see Section 11.1 for definition).

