8.3 Visits 3 and 4 (Weeks 1 and 2)

- Vital signs (within approximately 15 minutes prior to dosing and [pulse and blood pressure only] approximately 30 minutes after dosing)
- Weight (at Week 2 measurement used to reassess CZP dose according to [Table 7-1](#))
- CRP
- PRINTO/PRCSG standard joint examination
- Physician's Global Assessment of Disease Activity (VAS)
- CHAQ-parent reported
- Parent's Assessment of Arthritis Pain (VAS)
- Parent's Global Assessment of Overall Well-Being (VAS)
- Collection of JIA Pain VAS or FPS-R completed on Day 1 to Day 7
- Clinically Inactive Disease
- DMS
- JADAS
- Fatigue Assessment Scale
- Concomitant medications and procedures
- Adverse events
- IXRS contact
- CZP plasma concentrations (Week 1 only)

- Anti-CZP antibodies (Week 1 only)
- CZP administration (Week 2 only. Self/or parent/caregiver-administration under the supervision of the site staff for training.)

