11.2 PRINTO/PRCSG standard joint examination

The following 75 joints are to be examined for swelling, pain on motion (POM), tenderness, and limitation of motion (LOM) by the Investigator, another delegated physician, or an appropriately qualified medical professional (based on local requirements) who has had documented training on how to perform these assessments correctly. Preferably the same assessor should evaluate the study participant at each arthritis assessment, as per PRINTO/PRCSG guidelines. The individual with this delegated duty must be listed on Form 1572.

- Upper body (6) - bilateral temporomandibular, sternoclavicular, and acromioclavicular joints
- Upper extremity (34) - bilateral shoulders, elbows, wrists, metacarpals (MCP I, II, III, IV, and V), proximal interphalangeals (PIP I, II, III, IV, and V) and distal interphalangeals (DIP II, III, IV, and V)
- Lower extremity (30) - bilateral hips, knees, ankles, subtalar, tarsi, metatarsophalangeals (MTP I, II, III, IV, and V), and proximal interphalangeals (PIP I, II, III, IV, and V)
- Spinal (5) – cervical spine, thoracic spine, and lumbar spine, and bilateral sacroiliac joints

The assessment for LOM is made on 69 joints from the above list. The sternoclavicular, acromioclavicular, and sacroiliac joints are excluded. The assessment for swelling is made on

66 joints from the above list. The hip, subtalar, cervical spine, thoracic spine, lumbar spine, and sacroiliac joints are excluded. Artificial and ankylosed joints are excluded from both tenderness and swelling assessments.

Joint assessment will be based on a 2-point scale as unaffected (Grade 0) and affected (Grade 1).

These assessments are completed at Screening, Baseline, and every visit (including Unscheduled Visits that are related to dose change) through the Early Discontinuation/End of Treatment Visit.

11.3 Number of joints with active arthritis and number of joints with limitation of range of motion

The change in the number of joints with active arthritis and the change in the number of joints with limitation of range of motion will be assessed. Joint and joint motion assessments will be performed as part of the PRINTO/PRCSG standard joint examination.

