13.5 Planned efficacy and health outcomes analyses

Summary statistics will be presented for efficacy and health outcomes variables using the FAS.

All efficacy and health outcomes variables results will be presented overall and separately for the 2 CZP dose regimens (original CZP dose regimen, reduced CZP dose regimen).

The following efficacy variables are defined as secondary variables in this study:

- PedACR30, PedACR50, PedACR70, and PedACR90 response rates at Week 16 as compared to Baseline.

The following efficacy variables are defined as other variables:

- PedACR30, PedACR50, PedACR70, and PedACR90 response rates at every visit except Week 16 and Final Visit as compared to Baseline.

For PedACR30, PedACR50, PedACR70, and PedACR90, results will be presented overall and by Baseline weight strata, as well as by age (2 to 5 years, 6 to 11 years, and 12 to 17 years), by concomitant MTX use, and by anti-CZP antibody status.

- Change from Baseline in number of joints with active arthritis at every visit except Final Visit.
- Change from Baseline in number of joints with limitation of range of motion at every visit except Final Visit.
- Change from Baseline in Physician's Global Assessment of Disease Activity (VAS) at every visit except Final Visit.
- Change from Baseline in CHAQ at every visit except Final Visit.
- Change from Baseline in Parent's Assessment of Arthritis Pain (VAS) at every visit except Final Visit.
- Change from Baseline in Parent's Global Assessment of Overall Well-Being (VAS) at every visit except Final Visit.
- Ratio to Baseline in CRP at every visit except Final Visit.
- Change from Baseline in JADAS at every visit except Final Visit. The JADAS is a composite disease activity score including the Physician's Global Assessment of Disease Activity, the Parent's Global Assessment of Overall Well-Being, the active joint count, and CRP.
- Percentage of study participants with Clinically Inactive Disease (CID), as defined in Section 11.10, at every post-Baseline visit except Final Visit.

- Percentage of study participants with clinical remission on medication (CRM), as defined in Section 11.10, at every post-Baseline visit from Week 24 onwards except Final Visit.
- Time (in days) to CID.
- Time (in days) to CRM.
- Change from Baseline in DMS at every visit except Final Visit.

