13.6 Handling of dropouts or missing data

For all binary efficacy endpoints assessing response, study participants who withdraw early will be considered as non-responders from that time point onwards. The exception is efficacy data for study participants who withdraw after Week 56: Per Protocol Amendment 7, these will not be imputed (as nonresponse or missing) and will be analyzed as observed.

For continuous efficacy endpoints, missing assessments will be imputed using the last observation carried forward (LOCF) approach. These summaries will be supported by observed case (OC) analyses. Per Protocol Amendment 7, missing assessments after Week 56 will no longer be imputed and will be analyzed as observed.

Data collected after the taking of rescue medication will be treated as missing for continuous efficacy endpoints and non-response for binary efficacy endpoints in all analyses except where specifically stated otherwise. See Section 7.8.2 for a list of medications which would result in data at only the next scheduled visit (and not all subsequent visits) being treated as missing/non-response. These data will then be imputed as for any other missing data. The exception is any rescue medication use that is initiated after Week 56: Per Protocol Amendment 7, efficacy data after any rescue medication use initiated after Week 56 will not be imputed (as nonresponse or missing) and will be analyzed as observed.

Missing or partial dates for safety evaluations will be imputed and full details of these algorithms will be presented in the SAP.

As discussed in Section 13.2, Baseline is defined as the last nonmissing pretreatment measurement, therefore if available, data from the Screening visit will be used as Baseline values, if these data are missing at Week 0.

No further imputations of any other missing data are planned (eg, efficacy data missing at random [MAR]).

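### A treated child with no valid post-Baseline efficacy measurement leaves the PedACR denominator instead of counting as a non-responder, so any such case would raise the reported rate (minor)

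*Protocol*

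**What the plan says.** Three protocol rules together determine the PedACR denominator.

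- **Who is treated (13.1).** "The Safety Set (SS) will consist of all study participants in the ES who have received at least 1 dose of study medication".
- **Who is analysed for efficacy (13.1, 13.5).** "The Full Analysis Set (FAS) will consist of all study participants in the SS who have a valid Baseline and valid post-Baseline efficacy measurement". Section 13.5 then says: "Summary statistics will be presented for efficacy and health outcomes variables using the FAS". No other efficacy denominator is named.
- **How dropouts are scored (13.6).** "For all binary efficacy endpoints assessing response, study participants who withdraw early will be considered as non-responders from that time point onwards". Withdrawals after Week 56 are exempt and analysed as observed. Apart from the stated rules, no further imputation is planned.

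The endpoints concerned are the whole of the secondary variables (4.2): "Efficacy will be assessed by the PedACR30, PedACR50, PedACR70, and PedACR90 response rates at Week 16 as compared to Baseline". Section 13.5 presents them overall, by dose regimen, by Baseline weight stratum and by age group, among other subgroups. Section 13.2.1 defines each regimen subgroup from the Safety Set, as everyone who started that regimen and received at least one dose.

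**The concern.** The non-responder rule exists so that children who leave early are not quietly removed from a response rate. It can act only on children who are in the Full Analysis Set, and entry to that set depends on having a post-Baseline result. A treated child who leaves before giving one is therefore removed, although a child who leaves just after giving one counts as a failure.

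The direction of the effect is known. Compared with counting such a child as a non-responder, leaving the child out can only raise the rate or leave it unchanged. There is no control arm in which a similar loss could offset it.

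At stake is the accuracy of a set of descriptive single-arm rates. The protocol does rely on such rates: the futility rule used PedACR30 (13.7), and the dose rationale cites interim PedACR30 and PedACR50 (5.4.2).

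**Working it through.** **1. Reproduce the protocol's interim rates.** Section 5.4.2 gives Week 12 PedACR30 and PedACR50 of 77.3% and 67.5% overall, and 75.6% and 64.1% on the original regimen. Section 1 says the interim covered the first 163 participants. Section 13.8 says 78 were enrolled on the original regimen. I looked for whole-number denominators that give both percentages to one decimal.

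- Original regimen, denominators 50 to 78: only 78 fits (59/78 = 75.6%, 50/78 = 64.1%). That is the full number enrolled.
- Overall, denominators 120 to 163: 163 fits (126/163 = 77.3%, 110/163 = 67.5%). So does 154 (119/154 = 77.3%, 104/154 = 67.5%).

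The original-regimen rates show no exclusion, and the overall rates are consistent with none. On their own, the overall rates cannot rule out 163 − 154 = 9 exclusions. This reading assumes that the interim rates used the planned set and the planned non-responder scoring.

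**2. Formula.** Let N be the treated participants, k those left out of the Full Analysis Set, and p the reported rate in the N − k who remain. If the k are counted as non-responders, the all-treated rate is p × (N − k)/N. The upward bias is therefore p × k/N.

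**3. Inputs.** N = 186 is the planned total (13.8), with p = 77.3%. N = 78 + 30 = 108 is the original regimen including the Amendment 9 children, with p = 75.6%. The Week 12 rates stand in for Week 16. The protocol gives no value for k, so a range is shown. The roughly 20% dropout in 13.8 relates to 12 months of exposure and says nothing about loss before the first assessment.

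| k (assumed) | N = 186: all-treated rate, bias | N = 108: all-treated rate, bias |
|---|---|---|
| 1 | 76.9%, 0.4 points | 74.9%, 0.7 points |
| 2 | 76.5%, 0.8 points | 74.2%, 1.4 points |
| 3 | 76.1%, 1.2 points | 73.5%, 2.1 points |
| 5 | 75.2%, 2.1 points | 72.1%, 3.5 points |

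Using 163 + 30 = 193 in place of 186 leaves the effect at 0.4 points per child (77.3/193). A bias of 2 points in 186 needs about 5 exclusions (2/77.3 × 186 = 4.8). A bias of 5 points needs about 12 (5/77.3 × 186 = 12.0).

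**4. Small strata.** Section 5.1.2 sets a minimum of 10 participants per age category. In a stratum of 10 with 7 responders (illustrative numbers), leaving out one non-responder turns 7/10 = 70% into 7/9 = 78%.

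**The case against.** The strongest reply is that very few children can fall through. The core measures are taken at Week 1 and again at Week 2 (8.3), and at the Early Discontinuation Visit (8.7). Of the joint examination, Section 11.2 says: "These assessments are completed at Screening, Baseline, and every visit (including Unscheduled Visits that are related to dose change) through the Early Discontinuation/End of Treatment". Section 6.5 encourages children who stop study medication to remain in the study. Section 13.1 asks for a post-Baseline measurement, not a Week 16 result, so one usable Week 1 visit appears to be enough. This stands, and it limits the size of the problem.

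Three stronger readings are tempting, and the documents do not support them.

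- **That the PedACR rates are biased upward as a matter of fact.** The bias exists only if such children occur, and the interim rates fit full denominators.
- **That a child who stops after one dose because of an adverse event is automatically lost.** With a Week 1 or Early Discontinuation assessment, that child is in the set and is scored as a non-responder.
- **That the 30 Amendment 9 children are the main exposure.** One exclusion among 30 would be worth 75.6/30 = 2.5 points, but Section 13.5 plans no efficacy rate for that cohort alone. They are pooled with the other children who started the original regimen. The figure is illustrative only.

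It is also fair to say that the two rules do not contradict each other: one defines the set, the other scores children within it. That stands, but together they still leave the earliest losses unscored. The PedACR analyses are secondary and descriptive, and the primary safety summaries use the whole Safety Set (13.3), so they are unaffected. Finally, an SAP could add a Safety Set sensitivity analysis. That would help, but the protocol itself fixes the efficacy set and names no alternative.

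**Conclusion.** The point holds in conditional form and is minor. As written, the plan removes from the PedACR denominator any treated child without a valid post-Baseline efficacy measurement. If there are any, the reported rates are higher than they would be under the plan's own treatment of early withdrawals.

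The size rests on an assumed number of exclusions and on the Week 12 interim rates holding at Week 16. I read a valid measurement as any usable post-Baseline efficacy assessment. Section 13.1 does not define the term, and a stricter reading would exclude more children.

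No primary objective depends on this. The futility decision has been taken and would not plausibly change. For scale, bringing an overall 77.3% below 50% would need about 66 exclusions in 186 (186 × (1 − 50/77.3) = 65.7). That is not a re-run of the futility test, which concerned the reduced regimen at Week 16.

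**What to change.** In Section 13.1 or 13.5, for PedACR and the other binary responder endpoints up to Week 56:

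- use as denominator all Safety Set participants with a valid Baseline;
- score those who withdraw without any post-Baseline assessment as non-responders;
- report, overall and by regimen, how many Safety Set participants have no post-Baseline efficacy data.

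A child who has not withdrawn but has no valid assessment is not covered by the withdrawal rule. That child should be visible in the reported count. Continuous endpoints can stay on participants with data, with n reported.

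The change is workable because Baseline is the last nonmissing pretreatment value (13.2), so Screening values can fill a gap at Week 0, and core-set completeness is checked on site at Baseline (8.2). The cost is about one sentence in the protocol, carried into the SAP, and response rates that may be slightly lower. If the interim denominators were complete, as they appear to be, the interim rates already reported would not change.
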